SVR12	Sustained viral response at least 12 weeks after end of treatment
SMG	Management Group
TSC	Trial Steering Committee

SUMMARY/SYNOPSIS

Study Title	Evaluating Treatment as Prevention among People Who Inject Drugs in Dundee for HCV (E-raPiD-HCV)	
Study Design	The aim of this study is to conduct an evaluation of hepatitis C treatments in NHS Tayside in order to empirically test the “treatment as prevention” models. This will be done by analysing the records of patients who have been tested and treated for hepatitis C using NHS Tayside databases. There will be no interventions carried out as part of this study.	
Study Population	This study will monitor the target PWID population (we estimate approximately 2,800 individuals) as we intensify the number of treatments provided to this population and achieve levels of treatment that will test the “treatment as prevention” concept.	
Sample Size	Approximately 2,800 individuals	
Planned study Period	6 years	
Primary	Objectives To demonstrate treatment as prevention reduces HCV.	Outcome Measures HCV testing in NHS Tayside
Secondary	Objectives To develop the analytic framework that can be used to assess the impact of treatment as prevention, incorporating evidence from multiple sources and taking into account uncertainty and bias	Outcome Measures Numbers of patients engaged in treatment and SVR ₁₂ during the treatment phase
	Objectives To develop dynamic cost-effectiveness models of HCV treatment among PWID	Outcome Measures Costs of treatment pathways and infection rates
	Objectives Re-infection with HCV following treatment	Outcome Measures Annual routine offer of HCV testing
Inclusion Criteria	All individuals in NHS Tayside eligible for HCV testing and treatment according to Scottish Intercollegiate Guidelines Network guidelines.	
Exclusion Criteria	None	

1 INTRODUCTION

Hepatitis C is a blood-borne virus (HCV) that can seriously damage the liver and is spread mainly through blood-to-blood contact with an infected person. The “serious and significant public health risk” posed by HCV was recognised during a member’s debate in the Scottish Parliament in 2004. By December 2006, Health Protection Scotland estimated that 50,000 persons in Scotland had been infected with the Hepatitis C virus and that 38,000 were chronic carriers (1, 2). Currently, the greatest risk of acquiring the virus in the UK is through injecting drug use. In Scotland, it is estimated that over 85% of individuals who have Hepatitis C were infected in this way (3).

The outcome of HCV infection varies considerably between individuals. Some (up to 25%) are able to clear the infection spontaneously, whilst the remaining 75% become chronically infected (4). Within the subpopulation of chronically infected patients, some will develop serious liver disease, including cirrhosis and hepatocellular carcinoma, within a few years, whilst in others liver disease will not progress even over a period of more than forty years. Hepatitis C is often referred to as the ‘silent epidemic.’ Many who are infected are unaware of it, and often show no symptoms over a long period of time. While there is presently no vaccination for Hepatitis C, the recent introduction of protease inhibitor-based directly acting anti-viral treatments (DAA) has begun a new era in treatment of this disease (5). These new oral treatments are extremely safe, have shorter treatment regimens than previous drugs, and are effective, producing a cure in over 90% of cases providing compliance is adequate (6).

The advent of more effective DAA therapies raises the possibility of using therapy as prevention, turning the epidemic off at source, by targeting active infected drug users who are the main source of new infections.

Our modelling work shows that HCV treatment is a critical component to HCV prevention among people who inject drugs and is likely to be cost-effective compared to delaying treatment or treating non-PWID with mild or moderate disease (7-11). For example, we show in a number of settings with chronic HCV in PWID below 60% that treating 10-20 per 1000 drug users per year can reduce HCV prevalence by 50-90% over 10-15 years; that for every one PWID treated in the 20% chronic HCV setting 2 new HCV infections are averted. The scale of the benefit is inversely and exponentially related to prevalence of HCV in the population, the lower the prevalence the sooner and bigger the impact.

Current conventional treatment pathways focus on populations drawn from those known to drug problem services and former drug users. Treating people who are the most stable and with a low risk of relapse back into chaotic injecting will reduce future morbidity in the individual patients but may not achieve additional benefit in terms of averting future infections. Our recent work within Tayside has shown that we are able to test less stable, actively injecting drug users for Hepatitis C and then successfully treat them using both the conventional care pathway and non-conventional care pathways, such as needle exchange clinics (e.g. Eradicate study, completed February 2017; Advance study, started in January 2018, ongoing), community pharmacies (SuperDOTC study, December 2016 – January 2019. REACH HCV study, started February 2020, ongoing) and prisons (12). If the models are correct, this intensive treatment programme will effectively eradicate Hepatitis C from Tayside over the next few years. However, the models are not yet empirically tested and they make some assumptions that if violated may lead to over or under-estimation of the intervention effect. For example, the models assume that (a) heterogeneity in injecting risk and uptake of HCV testing and treatment will even out as PWID move and transition between high and low risk periods; and (b) that HCV transmission risk for susceptible PWID is similar for those that have achieved SVR or are untreated.

Our intensive treatment approach in Tayside provides an ideal opportunity to empirically test the “treatment as prevention” models. The current study will not involve direct recruitment or treatment of patients. Instead, it will evaluate the portfolio of care pathways currently being used to treat HCV in Tayside and test the hypothetical modelling to determine whether treatment of HCV will work as prevention of future spread of the virus.

2 BACKGROUND & RATIONALE

We have embarked on a series of studies that will dramatically increase the number of PWID with HCV infection who are being treated. This allows us to test empirically modelling data predicting treatment as prevention works for HCV infection. We are aiming to treat enough people actively injecting drugs who are infected with Hepatitis C in Tayside to reduce the prevalence in this population from approximately 29% to less than 10%. This will reduce the incidence of new infections from over 5% per annum to less than 1% per annum which we can detect with population surveillance techniques.

3 STUDY OBJECTIVES & OUTCOMES

Table 1: Primary Objectives and Outcome Measures

Primary Objective:	Outcome Measure:	Timepoint of outcome measured
To demonstrate treatment as prevention reduces HCV.	HCV testing in NHS Tayside	Annually

Table 2: Secondary Objectives and Outcome Measures

Secondary Objective:	Outcome Measure:	Timepoint of outcome measured
To develop the analytic framework that can be used to assess the impact of treatment as prevention, incorporating evidence from multiple sources and taking into account uncertainty and bias	Numbers of patients engaged in treatment and SVR ₁₂ during the treatment phase	Years 1-3
To develop dynamic cost-effectiveness models of HCV treatment among PWID	Costs of treatment pathways and infection rates	Year 5
Re-infection with HCV following treatment	Annual routine offer of HCV testing	Following treatment and subsequently annually for each PWID

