4.2 STUDY DESCRIPTION

The aim of this study is to conduct an evaluation of hepatitis C treatments in NHS Tayside in order to empirically test the “treatment as prevention” models. This will be done by analysing the records of patients who have been tested and treated for hepatitis C using NHS Tayside databases. Individuals working on this project will apply for Caldicott Guardian approval. As described previously, a number of strategies are being used to intensively identify and treat individuals with hepatitis C within Tayside.

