6 DATA COLLECTION & MANAGEMENT

6.1 DATA COLLECTION

Details of all patients who are undergoing or have completed HCV treatment in Tayside are entered into a clinical database as per standard care by specialist HCV nurses and this practice will continue as we intensify treatment rates through our clinical trials and NHS treatment pathways. Data in this database will form the source for treatment initiation and outcomes. Twice a year the number of patients treated and cured since last data extraction will be extracted with no patient identifiable information but with data on viral genotype, stage of liver disease, pathway of treatment delivery and current drug use status.

Data on infection rates from routine HCV testing within NHS Tayside is also collected in the virology service in Tayside for government reporting. On a six monthly basis we will extract data on known HCV negative patients who have been retested in that time period. The data extraction will consist of the date when they were last known to be negative, the date of re-test and the result of the test. No patient identifiable data will be used.

Population level data will be collected 6 monthly around the anniversary of the study commencement or to coincide with the NESI data collection cycles.

The source data will be accessed by the clinical care team and clinical data which is not patient identifiable entered into the study data management system which will be built within Excel and held on a University server that is GCP compliant; regularly backed-up, has access controls and updates to operating system and security software. Caldicott approvals will be obtained as required.

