6.2 DATA MANAGEMENT SYSTEM

Data management will be conducted in compliance with TASC SOPs on Data Management, including TASC SOP33 Data Management to GCP standards and TASC SOP53 Data Management Systems in Clinical Research.

The data management system (DMS) will be Excel. The data will be used to calculate the treatment rate and cure rate for the time period and the rate of new infection. The core data will then be destroyed. The anonymized dataset may be shared with colleagues in other UK Universities. The database is managed in line with all applicable principles of medical confidentiality and UK law on data protection, namely, the Data Protection Act 1998, which brought UK law into line with the EU Data Protection Directive. The Data Controller will be the University of Dundee and the Data Custodian will be the CI.

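### The primary and re-infection outcomes name testing, not infection; incidence seems intended but is not designated, and the retest extract cannot yield it for PWID

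*Combined protocol and SAP*

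**What the plan says.** All references are to the combined protocol and SAP.

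- **Section 3, Table 1 (repeated in the synopsis).** The primary objective is "To demonstrate treatment as prevention reduces HCV". The outcome measure beside it is "HCV testing in NHS Tayside", taken annually. No numerator, denominator, population, baseline or comparison is given.
- **Section 3, Table 2.** Re-infection after treatment is measured by "Annual routine offer of HCV testing".
- **Section 2.** There are two numerical aims. One is to "reduce the prevalence in this population from approximately 29% to less than 10" per cent; the other is to "reduce the incidence of new infections from over 5% per annum to less than 1% per annum".
- **Section 6.1.** Every six months the study will "extract data on known HCV negative patients who have been retested in that time period". The fields are the last-negative date, the re-test date and the result. The separate treatment extract does carry current drug use status. Population-level data are also to be collected, timed to the study anniversary or to NESI cycles.
- **Section 6.2.** The data will be used to "calculate the treatment rate and cure rate for the time period and the rate of new infection", after which the core data are destroyed.
- **Section 7.2.** Evidence synthesis and transmission models will measure the primary outcome, which is not named there.
- **Section 8.2.** A larger study will use HCV incidence measures collected in this one.

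**The concern.** A primary outcome should be a quantity whose change answers the objective. Testing is an activity, or the source from which such a quantity could be computed. An offer of a test is one step further from infection.

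Two things are at stake. First, section 2 offers two candidate quantities, and measurements recur annually over a planned six years. With neither candidate designated, the headline result could be picked once the values are known. Second, naming incidence would not be enough, because the extract that feeds it lacks the fields to restrict it to PWID or to identify people already cured. Core data are to be destroyed after calculation, so a quantity left out then may not be recoverable.

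**Working it through.** The plan has no calculated figure to reproduce: the 2,800 in section 7.1 is an estimate of the eligible population, without effect size, alpha or power. The check therefore mainly sets sections against one another.

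**1. Is a primary quantity designated anywhere?**

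| Place | Quantity | Called primary? |
|---|---|---|
| Table 1, synopsis | Testing | Yes, but not a measure of infection |
| Section 2 | Prevalence and incidence | No |
| Section 6.2 | Treatment, cure and new-infection rates | No; prevalence not listed |
| Section 7.2 | Primary outcome, unspecified | Not named |
| Section 8.2 | Incidence | No |

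The two candidates are not interchangeable. The prevalence target is a fall of at least 29/10 = 2.9-fold; the incidence target is at least 5/1 = fivefold.

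**2. Can the extract give incidence in PWID?** The two dates give time at risk and the result gives the event, so a rate can be formed. But section 4.11 lists eleven groups to be offered testing, only one of them defined by injecting, and the retest fields do not say who belongs to which. With w the PWID share of retest person-time:

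pooled rate = w × (PWID rate) + (1 − w) × (rate in others)

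Neither w nor the rate in others is given. As a limiting assumption, set the rate in others to 0:

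| w (assumed) | Pooled, PWID at 5% | Pooled, PWID at 1% |
|---|---|---|
| 100% | 5.0% | 1.0% |
| 50% | 2.5% | 0.5% |
| 20% | 1.0% | 0.2% |

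At w = 1/5 the pooled figure sits at 1% with no change in PWID. A shift in w between years would also move it.

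**3. Can first infection be separated from re-infection?** Section 6.1 does not say whether someone cured by treatment counts as known negative. If so, the two kinds of infection are mixed without a flag. If not, the retest extract holds no re-infection data. The treatment and retest extracts carry no identifiers, and no key joining them is described.

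**4. Is a defined outcome feasible?** The normal-approximation formula for two proportions, with p̄ the mean of p₁ and p₂, is

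n = [1.96√(2p̄(1−p̄)) + 0.842√(p₁(1−p₁) + p₂(1−p₂))]² / (p₁ − p₂)²

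Two-sided alpha 0.05, 80% power, independence and one year at risk per retest are all assumed.

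- Incidence 5% v 1%: (0.473 + 0.202)² / 0.0016, about 285 per period.
- Prevalence 29% v 10%: (1.098 + 0.458)² / 0.0361, about 68 per period.

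Uninfected people number 2,800 × 0.71 = 1,988 at 29% prevalence, and 285/1,988 is about 14%. This looks attainable, but the documents give no number of retests.

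**The case against.** The strongest reply is that Table 1 merely names the data source. Section 6.1 extracts results rather than test counts, section 6.2 plans a new-infection rate, section 8.2 calls what is collected incidence, and section 2 says the fall in incidence is detectable by surveillance. Section 4.9 also describes the study population as the PWID of Tayside. This stands as evidence of intent. It does not designate a primary quantity, and the retest fields cannot enforce the restriction in section 4.9.

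The list in section 6.2 need not be exhaustive: costs are a Table 2 outcome and are absent from it too. NESI-cycle data are collected and could supply prevalence. That also stands, so prevalence is uncommitted rather than impossible. An anonymised dataset may be shared, but it could not supply fields that were never extracted.

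A reader might infer that the study cannot show a fall in HCV, or that its measure would move the wrong way as testing grows. The documents support neither. Section 4.2 says that "a number of strategies are being used to intensively identify and treat individuals with hepatitis C within Tayside", but rising test volume is an inference and no volumes are given. A count of tests or of positives is not what section 6.2 plans to calculate. Even for a count of new positives, at the section 2 targets retest coverage would have to rise more than (1,988 × 5%) / (2,520 × 1%) = 99.4/25.2 = 3.9-fold before the count rose, where 2,520 is 2,800 × 0.90.

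**Conclusion.** The point holds as a defect of definition and of data fields. The primary and re-infection outcomes as written do not measure infection, no section chooses between incidence and prevalence, and the retest extract as specified cannot give incidence in PWID or separate re-infection. It goes beyond missing detail because correcting Table 1 alone would leave the named quantity uncomputable.

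No single size can be given, since the PWID share of retests is not stated. The dilution figures assume no new infections outside PWID and show what pooling could do, not what it will do. The conclusion also assumes that the field list in section 6.1 is complete and that the incidence target refers to PWID, as the context in section 2 indicates. The study itself remains capable of showing a fall in HCV once these items are settled.

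**What to change.** 1. In Table 1 and the synopsis, name the primary outcome as incidence of new HCV infection per 100 person-years among known-negative PWID who are retested. Judge it against the incidence target in section 2 and estimate it within the evidence-synthesis framework of section 7.2. A fixed contrast with a period before treatment was intensified should not be prescribed, because the documents name no retest data for such a baseline.
2. Name prevalence of current HCV infection among PWID at each NESI round as a second outcome, and add it to the calculations in section 6.2 before core data are destroyed.
3. In Table 2 and the synopsis, replace the re-infection measure with new infections per 100 person-years after SVR12.
4. Add non-identifiable indicators for PWID status and prior SVR12, with its date, to the six-monthly retest extract. State whether PWID means current or past injecting, and whether known negative includes people cured by treatment.
5. Report testing volume only as a process measure. It helps in judging who is retested, a selection that the new definition does not remove.

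The cost is two or three extra fields in an extract made by the clinical care team, possibly a Caldicott update, and a commitment in advance to one primary quantity.

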4 STUDY DESIGN

4.1 INTERVENTION

There is no intervention associated with this study.

4.2 STUDY DESCRIPTION

The aim of this study is to conduct an evaluation of hepatitis C treatments in NHS Tayside in order to empirically test the “treatment as prevention” models. This will be done by analysing the records of patients who have been tested and treated for hepatitis C using NHS Tayside databases. Individuals working on this project will apply for Caldicott Guardian approval. As described previously, a number of strategies are being used to intensively identify and treat individuals with hepatitis C within Tayside.

4.3 STUDY FLOWCHART

There will be no interventions carried out as part of this study. The timepoints for measurements are shown in Table 2.

4.4 STUDY MATRIX

There will be no interventions carried out as part of this study. The timepoints for measurements are shown in Table 2.

4.8 INCIDENTAL FINDINGS

4.9 STUDY POPULATION

The entire PWID population in Tayside (we estimate approximately 2,800 individuals)

4.10 NUMBER OF PARTICIPANTS

Approximately 2,800 individuals

4.11 INCLUSION CRITERIA

Data will be included from NHS Tayside NESI and treatment databases so the inclusion criteria will be all those eligible for HCV testing and treatment in NHS Tayside.

Scottish Intercollegiate Guidelines Network (SIGN) guidelines recommend that the following groups should be offered testing :

- patients with an otherwise unexplained persistently elevated alanine aminotransferase
- people with a history of injecting drug use
- people who are human immunodeficiency virus (HIV) positive
- recipients of blood clotting factor concentrates prior to 1987
- recipients of blood and blood components before September 1991 and organ/tissue transplants in the UK before 1992
- children whose mother is known to be infected with HCV
- healthcare professionals following percutaneous or mucous membrane exposure to blood which is, or is suspected to be, infected with HCV
- people who have received medical or dental treatment in countries where HCV is common and infection control may be poor
- people who have had tattoos or body piercing in circumstances where infection control procedure is, or is suspected to be, suboptimal
- people who have had a sexual partner or household contact who is HCV infected.
- Anyone who believes themselves to be at risk.

5 PARTICIPANT SELECTION AND ENROLMENT

5.1 IDENTIFYING PARTICIPANTS

Individual participants will not be consented into this trial. In accordance with the inclusion criteria, participants will be identified and analysed using NHS Tayside databases (following Caldicott approval).

6 DATA COLLECTION & MANAGEMENT

6.1 DATA COLLECTION

Details of all patients who are undergoing or have completed HCV treatment in Tayside are entered into a clinical database as per standard care by specialist HCV nurses and this practice will continue as we intensify treatment rates through our clinical trials and NHS treatment pathways. Data in this database will form the source for treatment initiation and outcomes. Twice a year the number of patients treated and cured since last data extraction will be extracted with no patient identifiable information but with data on viral genotype, stage of liver disease, pathway of treatment delivery and current drug use status.

Data on infection rates from routine HCV testing within NHS Tayside is also collected in the virology service in Tayside for government reporting. On a six monthly basis we will extract data on known HCV negative patients who have been retested in that time period. The data extraction will consist of the date when they were last known to be negative, the date of re-test and the result of the test. No patient identifiable data will be used.

Population level data will be collected 6 monthly around the anniversary of the study commencement or to coincide with the NESI data collection cycles.

The source data will be accessed by the clinical care team and clinical data which is not patient identifiable entered into the study data management system which will be built within Excel and held on a University server that is GCP compliant; regularly backed-up, has access controls and updates to operating system and security software. Caldicott approvals will be obtained as required.

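### The half-yearly extract cannot separate early stopping or a missing SVR12 test from treatment failure or a result not yet due, and the cure rate has no stated denominator

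*Combined protocol and SAP*

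**What the plan says.** Section 6.1 describes three sources.

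- **Treatment database.** "Details of all patients who are undergoing or have completed HCV treatment in Tayside are entered into a clinical database". The protocol adds: "Data in this database will form the source for treatment initiation and outcomes". The extract is defined as follows: "Twice a year the number of patients treated and cured since last data extraction will be extracted with no patient identifiable information". Four descriptive fields go with these counts: genotype, liver stage, treatment pathway and drug-use status.
- **Virology service.** Every six months, "we will extract data on known HCV negative patients who have been retested in that time period". The fields are the date last known negative, the re-test date and the result.
- **Population-level data.** These are collected six-monthly or in step with the NESI cycles. Section 4.11 also names NESI as a source.

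Section 6.2 then says: "The data will be used to calculate the treatment rate and cure rate for the time period and the rate of new infection". It gives no numerator, no denominator and no rule for a missing SVR12, and has the core data destroyed afterwards. Section 7.2 adds only a general commitment to take account of uncertainty and bias. Table 2 lists numbers engaged in treatment and SVR12 as an outcome for years 1 to 3. The abbreviation list defines SVR12 as a response at least 12 weeks after treatment ends.

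**The concern.** Cure is a natural input to the evidence synthesis and transmission models that section 7.2 uses for the primary objective. The Introduction makes the expected cure conditional, "producing a cure in over 90% of cases providing compliance is adequate", and describes a group in whom incomplete treatment and missed follow-up are plausible: "we are able to test less stable, actively injecting drug users for Hepatitis C and then successfully treat them", through needle exchanges, pharmacies and prisons among other routes.

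If untested patients are silently counted as failures, the cure rate is too low. If they are silently left out, it may be too high for the population that actually started. The reader of the result could not tell which had happened. A mismatch between modelled and observed infection might then be put down to transmission assumptions when part of it came from how missing results were handled. Table 2 also lists pathway costs as an outcome. If missing results differ between pathways, cost per cure by pathway would be affected too, although the plan neither gives evidence of such a difference nor commits to comparing cure by pathway.

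**Working it through.** The plan contains no cure-rate calculation to reproduce. The check has three steps.

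**1. What each extract can show, using only the fields listed in section 6.1**

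| State of a patient who started treatment | Treatment extract | Virology extract |
|---|---|---|
| SVR12 achieved | treated, cured | only if retested later as a known negative |
| Viraemic at SVR12 | treated, not cured | not by virtue of treatment |
| Stopped early, no SVR12 test | treated, not cured | not by virtue of treatment |
| Completed, SVR12 due, not tested | treated, not cured | not by virtue of treatment |
| Died or left before SVR12 | treated, not cured | not by virtue of treatment |
| On treatment, or SVR12 not yet due | treated, not cured | not by virtue of treatment |

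This takes the reading most favourable to the plan, that every starter is counted as treated. Five different states still share one entry. Genotype, liver stage, pathway and drug-use status do not separate them, and the virology fields carry no treatment information.

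**2. Why results not yet due need their own code**

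Assume starts are spread evenly over a 26-week window. With treatment lasting D weeks, the share of starters who cannot yet have an SVR12 at extraction is min(1, (D + 12)/26).

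- D = 0 (the floor): 12/26 = 46%
- D = 8 (assumed): 20/26 = 77%
- D = 12 (assumed): 24/26 = 92%

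Counting everyone without a result as not cured would therefore turn many pending patients into failures. The same lag means that those treated and those cured since the last extraction are largely different people.

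**3. How wide the uncertainty could be**

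Let c be cure among those tested and u the share of starters, with SVR12 due, who have no result. Take c = 0.90, the edge of the Introduction's figure of over 90%. The documents give no value for u, so 5% to 30% is assumed.

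- Lower bound (missing = not cured): c(1 − u)
- Upper bound (missing = cured): c(1 − u) + u

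| u (assumed) | Rate among tested | Lower bound | Upper bound |
|---|---|---|---|
| 5% | 90% | 85.5% | 90.5% |
| 10% | 90% | 81% | 91% |
| 20% | 90% | 72% | 92% |
| 30% | 90% | 63% | 93% |

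The width equals u. The rate among those tested lies inside the range, so it is not an upper bound.

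For scale in people: section 2 gives 29% prevalence and section 7.1 gives 2,800 individuals, so 0.29 × 2,800 = 812 infected. If all 812 started treatment, 5% to 30% without a result would be 41 to 244 people.

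**The case against.** Three objections have force.

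**Starters are probably in the database.** Anyone who begins treatment is undergoing it when entered, section 6.1 calls the database the source for treatment initiation, and the extract counts patients over an interval rather than by status on one day. A reader might infer that the cure rate covers completers only. The documents do not support that. Cured over treated could well be an all-starters rate with missing counted as not cured. What stands is that the rate is undefined and that the missing group cannot be isolated.

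**There is a third source.** A reader might infer that patients still infected after stopping vanish from the study. NESI and the population-level data may show current infection in aggregate whatever the treatment history, and Table 2 has testing offered after treatment and then annually. This is fair. But these data are not described as identifying treated patients, so they cannot correct the cure rate.

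**The effect on the prevalence target is not shown.** Section 2 aims for below 10%, that is, fewer than 280 infected (0.10 × 2,800), or 812 − 280 = 532 net cures at the 10% line. Assume 600 starts, 92% cure among completers with a test, and no new infections. Cures are 552 and prevalence is (812 − 552)/2,800 = 9.3%. If 10% of starters are unassessed and none is cured, cures fall to 600 × 0.90 × 0.92 = 497 and prevalence is 11.3%. A reader might infer that the target conclusion turns on this group. But 600 sits just above the break-even of 532/0.92 = 578 starts. With 700 starts and the same 10%, cures are 580 and prevalence is 8.3%. With 812 starts and 25% unassessed and uncured, cures are 560 and prevalence is 9.0%. Moreover, the plan does not derive prevalence by subtracting recorded cures. That inference should not be drawn.

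**Conclusion.** The point holds as a gap in the extract and in the definition of the cure rate. On the fields listed, early stopping and a missing SVR12 cannot be told apart from failure or a pending result, and section 6.2 sets neither a denominator nor a missing-result rule. Because the core data are destroyed once the rates are calculated, the group may not be recoverable later from the study's own data.

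The size is unknown. The 81% to 91% range at 10% missing, and the 63% to 93% range at 30%, rest on an assumed share without a result and on 90% cure among those tested. They show sensitivity and are not a forecast. The documents do not show that the cure rate is wrong, that the source database omits early stoppers, or that the conclusion on the 10% prevalence target depends on this group. This is a worthwhile, inexpensive improvement and not a flaw that defeats the study.

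**What to change.** **Section 6.1.** Define the extract as every patient who starts treatment, grouped by start-date cohort, with one de-identified outcome code per course:

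1. SVR12 achieved
2. viraemic at SVR12
3. stopped early without an SVR12 test
4. completed without an SVR12 test although due
5. died or left Tayside
6. still on treatment, or SVR12 not yet due

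A course with an SVR12 result should be coded by that result, whether or not treatment was completed. Code 6 should be updated at later extracts.

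**Section 6.2.** Define the cure rate among all starters whose SVR12 is due, overall and by pathway. Report missing counted as not cured as the lower bound and missing counted as cured as the upper bound. Give the rate among those tested as a separate figure. Carry the range into the evidence synthesis in section 7.2, and require the codes to be final before the core data are destroyed.

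**Cost.** One coded field and a cohort label in the half-yearly extract, updating of pending courses, and short wording changes; no extra visit, test or identifiable data. The downside is that the cure rate becomes a range and may look less favourable.
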